
 To assess proportion of subjects (subset of subjects) cleared from colonization (present/absent) through Day 85. 	
 B. pertussis clearance following study vaccination (subset of subjects at varying time points through Day 85).

Mucosal secretory immunogenicity (S-IgA) (optional substudy only)
 
Note that S-IgA objectives and endpoints for the overall study (as noted above) will also be analysed for the optional substudy and will be considered exploratory.
	
Exploratory objectives	Exploratory endpoints

 To evaluate mucosal immunity of individual and combinations of pertussis antibodies (eg, WCE, PT, FHA and PRN and other known anti-pertussis mucosal antibodies) are relational to protection against colonization (BPZE1, BPZE1 + Boostrix, BPZE1 and BPZE1 + Boostrix, Boostrix control). To measure BPZE1 induction of mucosal immunity (S-IgA) at Day 113 by treatment group; and to assess if induction of a boost response (relative to Day 85 response) is observed for those subjects with prior BPZE1 vaccination (BPZE1, BPZE1 + Boostrix). To assess if Day 113 response and longer-term durability through Day 169/EOS (absolute GMT) is altered with re-vaccination/attenuated challenge when compared to those subjects who did not participate in the substudy, relative to each randomized treatment group (BPZE1, BPZE1 + Boostrix, Boostrix). 	
 Induction of mucosal S-IgA at Day 29 or 85 (tested independently) compared by protection against colonization (Colonizers/Non-colonizers) by treatment group (BPZE1, BPZE1 + Boostrix, BPZE1 and BPZE1 + Boostrix, Boostrix control). Induction of mucosal S-IgA (WCE, PT, FHA, PRN and any additional anti-pertussis mucosal antibodies identified during assay development) at Day 113 compared with Day 85 following BPZE1 attenuated challenge by treatment group (BPZE1, BPZE1 + Boostrix). Induction of mucosal S-IgA at Days 113 and 169/EOS (tested independently) in subjects who participated in the substudy compared with subjects who did not participate in the substudy by treatment group.
--	---

Serum immunogenicity (IgA and IgG) (optional substudy only): WCE, PT, FHA, PRN, and any additional anti-pertussis antibodies identified during assay development using GMT and GMFR unless otherwise stated.

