3.1 Study Design

This is a multi-centre, randomized, observer-blinded, placebo- and active comparator-controlled trial with a 6-month safety follow-up after first study vaccination. After signing the informed consent form (ICF; or providing assent when necessary) and meeting all inclusion and none of the exclusion criteria, eligible subjects will receive an intranasal vaccination with either BPZE1 vaccine or formulation buffer (placebo) via the MAD and an intramuscular (IM) injection of either Tdap vaccine (i.e., Boostrix) or sterile normal saline (placebo) on Day 1. To maintain the blind, placebo vaccination via intranasal and IM routes, using formulation buffer and normal saline, respectively, will be included, and an unblinded team will manage vaccine logistics, preparation, and administration (when needed to maintain blinding) but will not be involved in study-related assessments or have subject contact for data collection after study vaccination.

Approximately 360 subjects will be enrolled and randomly assigned (1:1:1) to 1 of 3 treatment groups (refer to Table 3-1) to contribute to safety and efficacy assessments. Enrolment will be operationally managed at the study level to maintain a minimum number of subjects enrolled in 2 age groups: 6 to 10 years, inclusive; and 11 to 17 years, inclusive. It is estimated that a 10% dropout rate will occur, allowing for approximately 108 evaluable subjects per treatment group.

Table 3-1 Dosing Scheme

Treatment Group	n	Intranasal Vaccination ^a (Day 1)		IM Vaccination ^b (Day 1)	
		BPZE1	Placebo	Boostrix	Placebo
A	120	X	-	-	X
B	120	X	-	X	-
C	120	-	X	X	-

^a Intranasal application of ~0.4 mL per nostril (0.8 mL total volume delivered). Intranasal vaccination will occur prior to IM vaccination.

^b IM injection of 0.5 mL to the deltoid region.

All subjects will be monitored for at least 30 minutes after final study vaccination. On Day 1, intranasal vaccination will occur prior to IM vaccination with a minimum of 10 minutes (minimum of 30 minutes for subjects in the safety lead-in cohort of 11 to 17 year olds)

between intranasal and IM vaccinations. Immediate reactogenicity will be assessed at 30 minutes (+30 minutes) after the last study vaccination of the Day (ie, after IM vaccination on Day 1, after nasal vaccination on Day 85), prior to release from clinical observation.

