All subjects will record maximum daily reactogenicity in a subject diary for 7 consecutive days starting the day following any study vaccination (retrospective of the highest value in the previous 24 hours). Subject diaries will be age-adjusted as appropriate. Local (arm; after IM injection only), nasal/respiratory, and general systemic reactogenicity events will be recorded, including start and stop dates and including any actual measurements (ie, body temperature, redness and/or swelling at the injection site). Trained clinical staff will review the information from the subject diary with the subjects at the following visit and apply a standard toxicity grade to any reactogenicity event. Subjects will be instructed that should they have reactogenicity with a potential toxicity grade 3 at any time, they should contact the site on the same day and be seen or referred to a qualified medical facility within 24 hours.

As this is the first study of BPZE1 in school-age children, a staggered enrolment is planned. The first 45 subjects enrolled will be in the older age group (11 to 17 years, inclusive) and designated the safety lead-in cohort. Reactogenicity will be reviewed with these subjects during a supplemental visit 7 days following first study vaccination. After reactogenicity for the safety lead-in cohort is reviewed by the medical monitor, medical lead, and Safety Monitoring Committee (SMC) chairman (with appropriate consultation with investigators, if needed), the remainder of subjects will be enrolled.

All AEs will be monitored through 28 days after any study vaccination; all MAAEs will be monitored through 84 days following any study vaccination; and all AESIs and SAEs will be monitored through Day 169/EOS. Due to COVID-19 pandemic, a SARS-CoV-2 infection (confirmed by testing within the public health system) and any associated symptoms will be collected on a unique COVID-19 electronic case report form (eCRF) through Day 169/EOS if the COVID-19 pandemic remains ongoing in the region or if there are mass vaccinations using a COVID-19 vaccine during study conduct. Vaccines received outside of the study will be specifically queried at each visit and recorded through Day 169/EOS.

An informational card will be provided to all subjects indicating their participation in this vaccination study to prevent subjects from inadvertently receiving any scheduled/planned Boostrix-containing vaccines (tetanus, pertussis, diphtheria) during study conduct. Any

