enrolled subject who does not receive Boostrix during the study will be offered Boostrix at the conclusion of the study (following unblinding); this Boostrix ‘catch-up’ will be provided outside of the study schedule, at the discretion of the investigator, with vaccine provided by the sponsor.

Nasal and blood samples for immunogenicity assessments will be collected before vaccination and at selected time points following study vaccination. Mid-turbinate/nasopharyngeal sample collections will occur at selected time points following study vaccination to assess initial colonization (safety lead-in cohort only, Day 8) and to assess for clearance (remainder of cohort, either Day 29 or Day 85). A subset of subjects will also have the option to provide extra blood for cellular-mediated immunity assessments at baseline and Day 8 (safety lead-in cohort) and Days 85 and 113 (subgroup optional in substudy).

Due to the uncertainty with movement and/or isolation practices associated with the COVID-19 pandemic, telemedicine and remote sampling may be initiated with proper investigator and/or medical oversight.

The primary database lock will occur after all data are clean and all planned study procedures through Day 169/EOS (6 months) are complete. An interim database lock may occur after all subjects have completed Day 29 and sample testing for all primary and select secondary immune endpoints have been completed (mucosal and serum), but results will only be provided at treatment assignment level to maintain the blind. The site and those interacting directly with the site or subject data (eg, contract research organization [CRO], laboratories) will remain blinded to subject assignment until EOS or end of sample testing, depending on the activities of the associated entities.

Vaccination pause rules (refer to Section 6.5) will be in place with a review by the SMC initiated if any rule is met. In addition, the medical monitor and medical lead are empowered to request a review by the SMC (refer to Section 11.1.1.1) at any time for any safety reason.

3.1.1 Substudy: Attenuated Challenge With BPZE1 Following Prior Vaccination with BPZE1, BPZE1 + Boostrix, or Boostrix Alone

This is an optional open-label substudy in which enrolled subjects may elect to participate at any time from the day of enrolment through Day 85. A separate signed ICF (and separate

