5.1 Method of Assigning Subjects to Treatment Groups

Subjects will be randomly assigned to 1 of 3 treatment groups, in a 1:1:1 ratio, as presented in Table 3-1, and operationally managed to maintain a minimum number of subjects enrolled in 2 age groups: 6 to 10 years, inclusive; and 11 to 17 years, inclusive. A staggered enrolment is planned: the first 45 subjects enrolled will be in the older age group of 11 to 17 years, inclusive, and designated the safety lead-in cohort. After reactogenicity for the safety lead-in cohort is reviewed by the medical monitor, medical lead, and SMC chairman (with appropriate consultation with investigators, if needed), the remainder of subjects will be enrolled. An interactive response technology (IRT) system will be used to administer the randomization schedule centrally. The IRT system will also be designed to distribute the full cohort into groups to provide mid-turbinate/nasopharyngeal samples for *B. pertussis* culture or PCR on Day 29 or 85; however, if a subject cannot provide a sample on Day 29 (for any reason), the subject should provide a sample on Day 85 (this will not be considered a protocol deviation). Biostatistics will generate the randomization schedule using SAS® software Version 9.3 or later (SAS Institute Inc, Cary, North Carolina) for the IRT, which will link sequential subject randomization numbers to treatment codes. The randomization schedule will be created by the dedicated randomization team, stored in a separate project area, and will be blinded to the project team with the exception of an unblinded team who will manage vaccine logistics, preparation, and administration, but will not be involved in

study-related assessments or have subject contact for data collection following study vaccination.

Enrolled subjects may participate in an optional substudy in which subjects may elect to participate at any time from the day of enrolment through Day 85. No randomization is planned for the substudy as all subjects participating in the open-label substudy will receive an intranasal re-vaccination/attenuated challenge with BPZE1 on Day 85. It is recognized this may introduce some subject bias due to the opt-in nature, but this has been deemed acceptable by the sponsor.

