7.4.3.3 Analyses of Secondary Safety Endpoints

The number and percentage of subjects will be summarized for each solicited AE by timepoint, severity grade, and treatment group. Additionally, solicited AEs will be analysed by taking the maximum severity through 7 days following any study vaccination to summarize the frequency and percentage of subjects reporting each local [if applicable; after IM injection only], nasal/respiratory, or systemic event. Mean response (for any measurement) and duration through 7 days following any study vaccination will be summarized daily using descriptive statistics. Solicited AEs will be reported separately following study vaccination on Day 85 in the substudy.

Adverse events will be coded by preferred term and system organ class using the latest version of MedDRA.

The following unsolicited AEs will be summarized as number and percentage of subjects reporting at least 1 event in each preferred term and system organ class and cross-tabulated by severity and relationship to study vaccination.

- All AEs through 28 days following first study vaccination and following re-vaccination/attenuated challenge (substudy) by severity and relationship to study vaccination, and by treatment group.
- All MAAEs through 84 days following first study vaccination and re-vaccination/attenuated challenge (substudy) by treatment group by severity and relationship to study vaccination, and by treatment group and time since study vaccination.
- All AESIs and SAEs through Day 169/EOS by treatment group by severity and relationship to study vaccination, and by treatment group and time since study vaccination.

Serious AEs will be summarized by detailed listing showing the event description, preferred term and system organ class, relevant dates (study vaccinations and AEs), severity, relatedness, and outcome for each event. Any SAE considered related to BPZE1 will be classified as a SUSAR.

The number and percentage of subjects with SARS-CoV-2 infections or AESIs associated with COVID-19 infection or SARs-CoV-2 vaccine-related events will be summarized, if the COVID-19 pandemic remains ongoing in the region or if there are mass vaccinations using a COVID-19 vaccine during study conduct.

The number and percentage of subjects with colonization or clearance by real-time PCR or *B. pertussis* culture following study vaccination (subsets of subjects) will be summarized over time using the methods outlined in Section 7.4.2 for proportions.

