- ^u Subjects not in the safety lead-in cohort will be randomly assigned (1:1) to provide mid-turbinate/nasopharyngeal samples on either Day 29 or Day 85; however, if a subject cannot provide a sample on Day 29 (for any reason), the subject should provide a sample on Day 85 (this will not be considered a protocol deviation).
- ^v Collection of an extra 20 mL of blood for cellular-mediated immunity may be an option in a select number of individuals who are in the substudy (up to 45 subjects). This will not involve extra venipuncture, but only collection of additional volume.
- ^w Medically attended AEs will be monitored through 84 days following any study vaccination.

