8.4. Analyses of Endpoints for the Optional Substudy

8.4.1. Analysis of Colonization Endpoints

Colonization summary tables will be produced based on the sample type (mid-turbinate swab and nasopharyngeal swab).

The analyses in this section of the colonization substudy will be based on the PP immunogenicity analysis set but include only subjects who are enrolled in the optional open-label substudy. A sensitivity analysis will be conducted using the Immunogenicity Analysis Set but include only subjects who are enrolled in the optional open-label substudy.

To assess if prior BPZE1 induced mucosal immunity substantially reduces colonization at Days 92 and 99, the proportion of subjects with colonization at Day 92 or Day 99 will be analyzed. The 2-sided 95% CI in the proportion of subjects with colonization at either Day 92 or Day 99 (*B. pertussis* culture or PCR) will be calculated using Agresti-Coull method and summarized by treatment groups (BPZE1, BPZE1 + Boostrix, BPZE1 and BPZE1 + Boostrix, Boostrix control). The likelihood ratio chi-square test will be used to compare the proportions between treatment groups.

Separate relative risks, which are defined as the ratio of two treatment group proportions, will be calculated for 1) BPZE1 vs. BPZE1 + Boostrix; 2) BPZE1 vs. Boostrix control; 3) BPZE1 + Boostrix vs. Boostrix control; 4) BPZE1 and BPZE1 + Boostrix vs. Boostrix control. The CI for relative risk will be computed using the likelihood ratio method.

The relative risk reduction (RRR) is defined as $RRR (\%) = (1 - RR) \times 100$. The CI for the RRR will be obtained by transforming the CI for the relative risk using $(1 - UL, 1 - LL)$, where UL denotes the upper limit of the CI for the RR and LL denotes the lower limit of the CI for the RR.

The hypotheses for the primary endpoint are:

H0: RRR $\leq 0\%$

HI: RRR $> 0\%$

Rejection of the null hypothesis demonstrates a statistically significant vaccine effect, (i.e., LL of the CI $> 0\%$), and will be considered to meet the pre-specified study success criterion.

Colonization at Day 8 safety lead-in group will be analyzed to determine specimen type. Colonization at Day 29 or Day 85 will be analyzed for clearance of BPZE1.

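### No child is scheduled for both a Day 8 swab and a pre-challenge Day 29 or Day 85 swab, so the clearance endpoint cannot separate children who cleared BPZE1 from children it never colonised

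*Protocol*

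**What the plan says.** The objective in protocol 2.2 is the proportion of a subset of subjects "cleared from colonization (present/absent) through Day 85". SAP 3.2.2.5 carries it as *B. pertussis* clearance, and SAP 8.4.1 states: "Colonization at Day 29 or Day 85 will be analyzed for clearance of BPZE1". Neither document makes *cleared* conditional on an earlier positive swab, or limits the label to BPZE1 recipients, although Group C receives intranasal placebo.

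Protocol 3.1 divides the swabs by cohort: "initial colonization (safety lead-in cohort only, Day 8) and to assess for clearance (remainder of cohort, either Day 29 or Day 85"). Footnote u to Table 13-1 confirms it: "Subjects not in the safety lead-in cohort will be randomly assigned (1:1) to provide mid-turbinate/nasopharyngeal samples on either Day 29 or Day 85". A missed Day 29 swab moves to Day 85. Footnote c releases lead-in children outside the substudy from Day 85 samples. The swab row of Table 13-1 is blank at SSV3, the substudy's Day 85 visit. The SAP schedule (13.1) repeats all of this.

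Two phrases point the other way. Protocol 5.1 has the IRT "distribute the full cohort into groups to provide mid-turbinate/nasopharyngeal samples" on Day 29 or 85, and protocol 3.1.1 has substudy participants take part in every Day 85 sample, nasal ones included.

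On analysis, protocol 7.4.3.3 says that subjects with colonization or clearance "following study vaccination (subsets of subjects) will be summarized over time using the methods outlined in Section 7.4.2 for proportions". SAP 8.4.1 does not repeat the over-time wording and uses the Day 8 swab to determine specimen type.

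**The concern.** To say that a child cleared a live organism, one must know that the child carried it. Here the swab meant to show initial colonization and the swab meant to show clearance come from different children. A negative at Day 29 or Day 85 therefore fits two histories: the vaccine took and was cleared, or it never took. Protocol 1.3.1.2 expects most subjects to clear within two weeks, so a single negative at Day 29 or later says little about which applies.

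This is the first study of a live vaccine in school-age children, and clearance is a stated safety objective. A table headed as a clearance rate would be read as a statement about colonised children, when its denominator is all vaccinated children who were swabbed.

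**Working it through.** The documents give no sample size, power or expected rate for this endpoint, so there is no planned figure to reproduce. The check has three parts.

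**1. Who is swabbed before any second dose**

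| Swab | Lead-in (45, aged 11–17) | Remainder (315, aged 6–17) |
|---|---|---|
| Day 8 | yes | no |
| Day 29 | no (footnote u) | half, randomised |
| Day 85, outside substudy | no (footnotes c, u) | other half, plus Day 29 transfers |
| Day 85, in substudy (SSV3) | blank cell | blank cell |

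A lead-in child who joins the substudy is next swabbed on Days 92 and 99, after the Day 85 BPZE1 challenge. Those swabs say nothing about clearing the first dose. Scheduled Day 8 + Day 29/85 pairs: 0. Scheduled Day 29 + Day 85 pairs: 0.

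**2. Numbers of BPZE1 recipients** (from 360 subjects, 1:1:1, two of three groups given BPZE1, 10% dropout)

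- Lead-in: 45 × 2/3 = 30.
- Remainder: (360 − 45) × 2/3 = 210, so 105 per swab day. After dropout, 105 × 0.9 = 94.5, taken as 94.
- Day 85 if all 120 substudy places fill in proportion (assumption) and SSV3 gives no swab: 105 × (1 − 120/360) × 0.9 = 63.

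**3. Effect of the missing pairing.** Let c be the share ever colonised (take) and p the share of colonised children still positive at the swab. Neither is in the documents; I use c = 0.5 to 0.7 and, for illustration, p = 0.20.

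*Some swabs positive.* Reported cleared = 1 − c × p; true clearance among colonised = 1 − p = 80%.

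- c = 0.5: 1 − 0.5 × 0.2 = 90%.
- c = 0.7: 1 − 0.7 × 0.2 = 86%.

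Seen from the observed side, if 5% of swabs are positive the table shows 95% cleared. Clearance among colonised is 1 − 0.05/c, which is 90.0% at c = 0.5 and 92.9% at c = 0.7. The never-colonised share of the negatives is (1 − c)/(1 − 0.05), which is 53% and 32%.

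*No swab positive.* The point estimate is 100% on either denominator. The upper 97.5% bound on persistence is 1 − 0.025^(1/n):

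| Denominator | n | Bound |
|---|---|---|
| All swabbed BPZE1 recipients | 94 | 3.8% |
| Colonised, c = 0.7 | 94 × 0.7 ≈ 66 | 5.4% |
| Colonised, c = 0.5 | 94 × 0.5 = 47 | 7.5% |
| All swabbed, Day 85, substudy full | 63 | 5.7% |

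The one planned look at early take is Day 8 in about 30 BPZE1 recipients. A result of 21/30 would have an Agresti-Coull 95% CI of 52.0% to 83.5%, too wide to correct the later figures well. It would also describe only 11–17-year-olds without the asthma and bronchospasm exceptions.

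**The case against.** The best defence is that the documents never define clearance as a positive followed by a negative. They score present or absent, in subsets, at varying times. For the practical safety question of whether the live organism is still detectable weeks after vaccination, all vaccinees are a proper denominator, and that proportion is validly estimable. Protocol 1.3.1.2 also reports that BPZE1 has always cleared in earlier studies, which makes 20% persistence look pessimistic. A Day 8 pairing would not settle matters either, since a child negative at Day 8 might already have cleared. All of this stands, and it is why the remedy is to the label and the table rather than to the sampling. It does not rescue the word *cleared*.

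Four stronger readings are tempting and are not supported:

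- *That the analysis will join Day 8, 29 and 85 into one curve.* Only protocol 7.4.3.3 speaks of a summary over time. SAP 1 makes the SAP govern where the two differ, and SAP 8.4.1 gives Day 8 a separate purpose.
- *That Day 29 and Day 85 are also incomparable.* Both draw on one 6–17-year pool randomised 1:1 to swab day. The contrast is sound apart from Day 29 transfers and substudy joiners. Only Day 8 against later days crosses cohorts.
- *That the plan will certainly overstate clearance.* This needs at least one positive swab and take below 100%.
- *That protocol 5.1 would yield paired data in the lead-in cohort.* Read literally it might, but footnotes c and u contradict it.

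**Conclusion.** The point holds as a mismatch between endpoint and sampling. Under Table 13-1 with footnotes c and u, no pre-challenge pair exists, and *cleared* cannot be told from never colonised, either for the single child or, when some swabs are positive, for the group percentage.

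The size depends on take and persistence, neither of which the documents give. At the assumed values above, the overstatement is 10 to 6 percentage points. With no positive swabs it is nil in the point estimate and shows only as a bound that is too tight for colonised children. The figure of 94 is reasonably firm for Day 29 but is an upper figure for Day 85, because substudy joiners have no scheduled SSV3 swab.

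The endpoint is secondary and descriptive, and the primary and key secondary analyses do not depend on it. It is still worth changing, because following the plan as written would put a clearance rate into the report that the data cannot support.

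**What to change.** - In protocol 2.2 and 7.4.3.3 and SAP 3.2.2.5 and 8.4.1, rename the endpoint to *B. pertussis* detected / not detected.
- Report it in BPZE1 recipients, separately at Day 29 and Day 85, by the swab day to which the child was randomised, with Day 29-to-Day 85 transfers on their own line. Show Group C separately if at all.
- Align protocol 7.4.3.3 with the SAP so that Day 8 is not joined to Days 29 and 85 as one time course, and note in the table that the Day 8 results come from different, older and more narrowly selected children.
- Reconcile protocol 5.1 (full cohort) and 3.1.1 (all Day 85 sampling) with footnotes c and u and the blank SSV3 swab cell.

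The cost is wording in both documents and one table shell; no new samples are needed. The downside is that the study can then claim only that the organism was not detected, not that it was cleared.

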assent when necessary) will be obtained prior to participation in the substudy. Subjects will be excluded from participating in the substudy if they meet additional exclusion criteria listed in Section 4.1.2.1. Temporary vaccination holding criteria are to be followed for the Day 85 vaccination.

Up to 120 enrolled subjects may participate in the substudy. The duration of the entire study will not change; however, additional visits/procedures starting on Day 85 will include the following:

- 3 additional visits (Days 92, 99, and 113)
- 1 additional intranasal vaccination (Day 85)
- Up to 3 additional nasal samples, including 2 of those needed for mid-turbinate/nasopharyngeal sample collection (Days 92 and 99) and 1 needed for leukosorb (Day 113). Subjects will contribute to all Day 85 sampling (systemic and nasal)
- Up to 2 additional blood samples (Days 85 [if not already assigned to provide] and 113, including blood for cellular-mediated and systemic immunity responses)
- 1 additional subject diary (subjects to record maximum daily reactogenicity [nasal/respiratory, systemic] in a subject diary for 7 consecutive days starting the day following study vaccination)
- 1 additional test for SARS-CoV-2 within 72 hours prior to Day 85 vaccination

All subjects participating in the open-label substudy will receive an intranasal re-vaccination/attenuated challenge with BPZE1 on Day 85. Subjects may have the planned re-vaccination/attenuated challenge deferred to a later date (up to 20 days) if pre-defined temporary exclusion criteria are met (Section 4.1.2.1) or for other personal reasons (eg, holiday, school schedule). Subjects will be monitored for at least 30 minutes after re-vaccination/attenuated challenge, with a post-vaccination evaluation for reactogenicity (nasal/respiratory, and systemic) completed prior to release from clinical observation.

Subjects will receive a subject diary on Day 85. All subjects (with assistance when needed) will record maximum daily reactogenicity in a subject diary for 7 consecutive days starting the day following re-vaccination/attenuated challenge (retrospective of the highest value in the previous 24 hours). Subject-reported symptom diaries will be age-adjusted as appropriate.

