13.1 Appendix: Schedule of Events

Table 13-1 **Schedule of Events**

Subject Population	Screening		Treatment Period							EOS	
	All Subjects	All Subjects	Safety Lead-In Subjects ONLY	All Subjects	Subjects NOT in Substudy	Subjects Participating in Substudy ONLY ^d			All Subjects		
Study Visit	Screening	V1	S1 ^b	V2	V3 ^c	SSV3	SSV4	SSV5	SSV6	Unscheduled ^e	EOS/Early Termination
Study Day	-30 to 1 ^a	1	8	29	85	85	92	99	113	-	169
Window allowance	30	0	+3	+7	+14	+20	+3	+2	+7	-	+30
Informed consent	X					X ^{f,g}					
Inclusion/exclusion criteria	X	X ^{f,g}				X ^{f,g}					
Demographic and baseline data ^h	X										
Medical history ⁱ	X	X ^{f,g}									
Concomitant medication ^j	X	X ^g	X	X	X ^k	X ^g	X	X	X	X ^k	X ^k
Concomitant vaccines ^l	X	X ^g	X	X	X	X ^g	X	X	X	X	X
Targeted physical examination ^m	X	X ^g	X	X	X	X ^g	X	X	X	X	X
Vital sign measurements ⁿ	X	X ^g				X ^g				X	
Urine pregnancy test ^o	X	X ^g				X ^g				X	
SARS-CoV-2 test for active infection (within 72 hrs prior to vaccination) ^p		X				X					
Study vaccination ^q		X				X					
Immediate reactogenicity		X ^r				X ^r					
Subject diary dispensed ^s		X				X					

Subject Population	Screening		Treatment Period								EOS
	All Subjects	All Subjects	Safety Lead-In Subjects ONLY	All Subjects	Subjects NOT in Substudy	Subjects Participating in Substudy ONLY ^d				All Subjects	
Study Visit	Screening	V1	S1 ^b	V2	V3 ^c	SSV3	SSV4	SSV5	SSV6	Unscheduled ^e	EOS/Early Termination
Study Day	-30 to 1 ^a	1	8	29	85	85	92	99	113	-	169
Window allowance	30	0	+3	+7	+14	+20	+3	+2	+7	-	+30
Subject diary reviewed ^f			X	X			X			X	
Nasal sampling for immunogenicity laboratory tests		X ^g		X	X	X ^g			X		X
Mid-turbinete/nasopharyngeal sampling for B. pertussis culture or PCR			X	X ^u	X ^u		X	X			
Blood sampling for immunogenicity laboratory tests		X ^g		X	X	X			X		X
Blood sampling for cellular-mediated Th1 and Th2 responses		X ^b	X			X ^v			X ^v		
Any TEAE (following most recent vaccination)		X	X	X		X	X	X	X	X	
Any MAAEW, AESI, or SAE (following first vaccination)		X	X	X	X	X	X	X	X	X	X
EOS form											X

^a Screening visit may occur on Day 1 prior to study vaccination.

- ^b Safety lead-in subjects (only) to complete procedures listed under Study Visit S1; PBMCs to be collected in a subset of subjects.

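### The schedule of events has no swab at the substudy's Day 85 visit, although footnote u and section 5.1 assign Day 85 clearance swabs without excepting substudy participants; up to about a third of the Day 85 swabs (about a sixth of all clearance swabs) could go uncollected.

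*Protocol*

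**What the plan says.** **Assignment of the swab.** Protocol section 5.1 states: "The IRT system will also be designed to distribute the full cohort into groups to provide mid-turbinate/nasopharyngeal samples". Footnote u of Table 13-1, repeated in SAP section 13.1, gives the rule: "Subjects not in the safety lead-in cohort will be randomly assigned (1:1) to provide mid-turbinate/nasopharyngeal samples on either Day 29 or Day 85". It adds a fallback: "if a subject cannot provide a sample on Day 29 (for any reason), the subject should provide a sample on Day 85". Neither place excepts substudy participants. Protocol section 3.1 describes these swabs as the clearance assessment for everyone outside the lead-in cohort.

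**Substudy text.** Section 3.1.1 says of participants: "Subjects will contribute to all Day 85 sampling (systemic and nasal". The same list places the additional swabs on Days 92 and 99.

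**Schedule.** In Table 13-1 the row that begins "Mid-turbinete/nasopharyngeal sampling for" is marked at S1 (Day 8), V2 (Day 29), V3 (Day 85), SSV4 (Day 92) and SSV5 (Day 99). It is empty at SSV3 (substudy Day 85). Footnotes c and d send non-participants to V3 and participants to SSV3. The SAP schedule has the same marks and the same gap.

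**Use of the swabs.** Clearance through Day 85 is a secondary safety endpoint (Protocol section 2.2). SAP section 8.4.1 analyses the Day 29 and Day 85 results for clearance.

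**The concern.** A child randomised to a Day 85 swab who then joins the substudy leaves the V3 column for the SSV3 column, where no swab is marked. The fallback for a missed Day 29 swab fails in the same way. Sites working from the table and sites working from footnote u would collect different data.

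At stake is the Day 85 part of a stated secondary safety endpoint, in what the protocol describes as the first study of BPZE1 in school-age children. The missing swabs would not be a random subset. Joining the substudy is voluntary and possible up to Day 85 itself, so an assigned swab could be cancelled on the day of the visit. Section 5.1 already accepts that opting in may introduce some bias.

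**Working it through.** The plan states no expected number of clearance swabs, so there is no figure to reproduce. The base counts agree with the plan's own: 120 × 0.9 = 108 evaluable subjects per group.

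**Inputs**
- Enrolment (Protocol 3.1): "Approximately 360 subjects will be enrolled and randomly assigned (1:1:1) to 1 of 3 treatment groups".
- Lead-in cohort (Protocol 3.1), swabbed on Day 8 and outside the Day 29/Day 85 split: "The first 45 subjects enrolled will be in the older age group (11 to 17 years, inclusive) and designated the safety lead-in cohort".
- Substudy size (Protocol 3.1.1), a ceiling: "Up to 120 enrolled subjects may participate in the substudy".
- Swab allocation 1:1 (footnote u).

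**Denominators**
- Subjects outside the lead-in cohort: 360 − 45 = 315. This is the number of clearance swabs over both days.
- Assigned to Day 85: 315 / 2 = 157.5.

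**Loss if sites follow the table**

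Swabs lost = (substudy participants outside the lead-in cohort) / 2.

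| Substudy | Participants outside lead-in | Lost | Share of Day 85 swabs (÷157.5) | Share of all clearance swabs (÷315) |
|---|---|---|---|---|
| 120, proportional uptake | 120 × 315/360 = 105 | 52.5 | 33% | 17% |
| 120, none from lead-in | 120 | 60 | 38% | 19% |
| 120, all 45 lead-in subjects join | 75 | 37.5 | 24% | 12% |
| 60, proportional uptake | 52.5 | 26.25 | 17% | 8% |
| Any size, sites follow footnote u | – | 0 | 0% | 0% |

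For the first row, a simulation (hypergeometric for lead-in membership, binomial for swab day, 100,000 draws) gives a 95% chance range of 42 to 63 swabs: 27% to 40% of Day 85 swabs and 13% to 20% of all.

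**Sensitivity, on assumed values**
- If 10% to 20% of Day 29 swabs move to Day 85, then with a full substudy and proportional uptake the loss is 157.5 × 1.1 / 3 = 57.75 to 157.5 × 1.2 / 3 = 63. That is still a third of Day 85 swabs, and 18% to 20% of all.
- If the plan's 10% dropout removes Day 85 swabs before the visit while the substudy still fills, the Day 85 base falls to 157.5 × 0.9 = 141.75. The loss is then 52.5/141.75 = 37% to 60/141.75 = 42% of Day 85 swabs. Of all swabs it is 52.5/299.25 = 18% to 60/299.25 = 20%.

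**The two BPZE1 groups.** There are 315 × 2/3 = 210 subjects outside the lead-in cohort, 105 of them assigned to Day 85. With a full substudy and proportional uptake about 35 are lost, which is 35/105 = 33% and 35/210 = 17%.

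**Is the blank an extraction error?** Probably not. The neighbouring rows for nasal and blood immunogenicity samples carry SSV3 marks, and the SAP schedule repeats the gap.

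**The case against.** The case against has four parts.

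- **The section 3.1.1 sentence proves little.** Table 13-1 schedules a nasal immunogenicity sample and blood at SSV3, and these would satisfy it. If it is read to include the swab, the text already requires the swab and nothing is lost. This stands: the sentence alone does not establish a contradiction. The conflict between footnote u with section 5.1 and the blank cell does not depend on it.
- **The additional swabs are limited to Days 92 and 99.** They are, but a footnote-u swab belongs to the main study and is not an additional one, so this does not explain the blank.
- **The consequence is slight.** The endpoint is descriptive, concerns subsets of subjects, and has no sample size, power or hypothesis attached. In the proportional full-substudy case about 105 Day 85 swabs and about 158 Day 29 swabs remain. This stands, and it keeps the point minor.
- **The loss is conditional.** It needs a well-filled substudy and sites that follow the table over footnote u. This also stands.

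A reader might also infer that no challenged child has any swab before the challenge, so that a Day 92 positive could not be told from residual carriage. The documents do not support that. V2 applies to all subjects, so participants assigned to Day 29 have a swab about eight weeks before the challenge, and lead-in participants have one at Day 8. Protocol section 1.3.1.2 describes clearance over 28 days, mostly within two weeks. Only a Day 85 pre-challenge swab is unscheduled, and restoring the assigned swabs would supply one for only about half of the participants outside the lead-in cohort.

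**Conclusion.** The inconsistency is real and appears in both schedules. The assignment rule covers substudy participants, while their only Day 85 visit carries no swab. If sites follow the table and the substudy reaches 120, about 53 to 60 swabs would not be collected: about a third of Day 85 clearance swabs and about a sixth of all clearance swabs. The range assumes uptake unrelated to swab day, with lead-in subjects joining in proportion or not at all.

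A reader might take the third as a share of all clearance swabs. It is not, because clearance is assessed on Day 29 and Day 85 together. Losing a third of 315 would need 105 of the 120 participants to be assigned to Day 85, against about 52.5 expected.

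The primary and key secondary analyses do not use these swabs and are unaffected.

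**What to change.** Reconcile Table 13-1 and SAP section 13.1 with footnote u and section 5.1. The swab row should be marked at SSV3, with footnote u and a before-vaccination note, for participants randomised to Day 85 or moved there after a missed Day 29 swab. State in section 3.1.1 that its sentence on Day 85 sampling includes this swab. If the blank was deliberate, footnote u, section 5.1 and the SAP's clearance analysis must instead state the exception and its effect on the Day 85 sample.

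The cost is a schedule correction. It needs no new randomisation. The swab is one the plan already assigns, at a visit that already has nasal sampling before the challenge. The burden is one swab for roughly half of the participants outside the lead-in cohort.
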